7.4. Trial intervention and additional imaging (CRAFT-RCT and CRAFT-IMG)

At time of recruitment for CRAFT-RCT women will be randomly assigned (1:1) to cerclage or surveillance. Randomisation will be carried out online via the RedCap web platform. Users will be assigned a personal identifier number. Due to the nature of the interventions, the study is not blinded to the care providers or patient. Recruiters and trial co-ordinators will not have access to the randomisation sequence. Women will be informed at time of recruitment to which arm they have been randomised. A 'minimisation' procedure, using a computer-based algorithm, will be used to avoid chance imbalances in important stratification variables. Stratification variables will be a) gestation, b) BMI <30 or ≥30 kg/m² c) risk factor (previous premature delivery <24 weeks, PPROM, late miscarriage or previous cervical surgery). Women will not know what treatment they will be allocated prior to recruitment. RedCap will write the randomisation program and hold the allocation code. Contact information will be obtained from the patient. Demographic measures such as ethnicity, BMI etc will be entered into the central trial database.

Following randomisation in CRAFT-RCT, the attending clinician will arrange for either a cervical cerclage (to be carried out within 7 days) or further observation as the randomisation indicates.

There is no “emergency code break” procedure as the trial is open label randomised trial. The method and materials used will be according to local protocols and clinician preference.

Indications for withdrawal of treatment (removal of cerclage):

- Participant request.
- Elective preterm delivery.
- Fetal membrane rupture.
- Symptomatic placenta praevia.
- Completion to 37 weeks gestation.

Indication for additional treatment (rescue/emergency cerclage):

- Exposed membranes or open cervix at 16⁺⁰-27⁺⁶ weeks gestation.

The final study visit will take place between 34+0 and 37+0 weeks gestation. For those in the cervical cerclage arm an appointment for removal will be made for 37 weeks as per local policies and practice. If delivery occurs prior to this time the research team will collect this outcome data. Apart from the final study visit (34+0 and 37+0 weeks), all trial visits will occur during routine clinic attendances according to local clinical protocols and clinician practice.

Participants of the imaging sub-study (CRAFT-IMG) will have a minimum of 1 advanced transvaginal ultrasound and 1 MRI up to a maximum of 3 MRIs and 3 advanced protocol transvaginal ultrasound scans (around 5 minutes longer than a cervical surveillance transvaginal ultrasound). The number carried out depends on the length of the pregnancy and patient’s availability. Where possible these will be co-ordinated with clinical appointments to minimise disruption. Participants will be offered reasonable reimbursement for their travel for these additional appointments.

8. Data analysis

CRAFT-OBS: This study will calculate prediction of preterm birth <37 weeks gestation in women with a previous CS in labour by observing clinical pregnancy outcomes. Where data is available the predictive value based on cervical length and quantitative fetal fibronectin will also be assessed. Results will be presented as both odds ratios and risk differences. Standard predictive statistics will be used for prediction of delivery <34 and <37 weeks gestation.

CRAFT-RCT: CRAFT-RCT: Statistical analysis of results will be undertaken by the research team and [name]. The primary analyses will be by intention to treat. The main outcome is delivery under 34 weeks. Secondary analyses will include secondary endpoints as per section 4.2. Standard predictive statistics will be used for prediction of delivery <34 weeks gestation (cervix ≤ 25 mm will be calculated along with area under the curve). We will also validate our current predictive tools of cervical length and fetal fibronectin in this population. Results will be presented as both odds ratios and risk differences, leading to number needed to treat (NNT) if appropriate, according to CONSORT guidelines. A subgroup analysis will be carried out according to other risk factors for preterm birth other than FDCS.

CRAFT-IMG: This sub-study will provide data on relationships between macro/ micro-structural cervical defects in pregnant women who have had a previous FDCS and a short cervix ≤ 25 mm, compared with those who have a cervix > 25 mm. Comparison will be made between the two groups. Relative efficiency of detection of cervical defects by MRI (and relationships with outcomes), will be compared to those identified by ultrasound. We will also assess changes in the cervix over time. This will be performed in conjunction with senior statistician [name]. Images will be assessed for: overt structural abnormalities in collaboration with radiologists using a structured proforma. Patients and clinicians will be informed of clinically significant findings. These images will be compared to TVUS images in order to ascertain whether there is any correlation in findings between the two modalities (ref 910).

Ultrasound data will be analysed contemporaneously at acquisition. MRI data will be assessed for cervical anatomical features and presence and location of overt lesions or disruptions on conventional imaging (blinded to the participant's history). Models will be fitted using the open-source toolkits for diffusion data by [name] and [name] (UCL)^{10,11}, to obtain quantitative maps of tissue composition and microstructure properties. We will analyse the different imaging findings between short and long cervixes and correlate it with their perinatal outcomes.

9. Study Governance

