Preterm birth (PTB), birth before 37 weeks gestation, has a global prevalence of 9.6% and over a million annual neonatal deaths. Recently, it has been observed FDCS are associated with recurrent, early premature births and late miscarriage (LM). Over 25% of all deliveries in the UK are by caesarean section (CS) and at least one in seven of these occur at full dilatation, affecting 20,000 women per year. These women have a six-fold increased incidence of subsequent preterm birth compared with women who undergo 1st stage CS earlier in labour, which equates to 2500 women per year in the UK. In women who lose a pregnancy, more than half will also go on to experience recurrent pregnancy losses in spite of current intervention. Prediction and management of these cases requires further understanding of its aetiology, assessment of current prediction strategies as well as clinical management.

Despite the emerging association between FDCS and the risk of PTB/LM, the risk following an in labour CS, not at full dilatation, is unknown. It is thought that late stage caesareans, from 7cm onwards, are likely to carry some risk of future preterm birth (3). Furthermore, our current predictive models of preterm birth based on transvaginal ultrasound and quantitative fetal fibronectin are not validated in this specific cohort of women. In this CRAFT study we will evaluate the risk of preterm birth in women with a previous history of caesarean section in labour.

Clinically, a short cervix (≤ 25 mm) on transvaginal ultrasound scan (TVS) during the second trimester identifies women at high risk of PTB/LM. These women may benefit from prophylactic treatment such as a cervical cerclage but currently it is not part of routine care. At present it is unknown whether the ≤ 25 mm cut-off is a reliable predictive measure of risk in women following in labour CS. The mechanism of late miscarriage and early premature births < 34 weeks needs to be further understood with the imaging modalities available to us.

There will be three components to the CRAFT project: 1) CRAFT-OBS 2) CRAFT-RCT and 3) CRAFT-IMG Study

CRAFT-OBS: a study of risk and management in women with a history of CS in labour

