1.1. Background

Preterm birth (PTB), defined as birth less than 37⁺⁰ weeks gestation, is a significant health issue and is the most important single determinant of adverse infant outcome with regards to survival and quality of life(4). Morbidity is inversely correlated to gestational age, and the most significant adverse outcomes are associated with very preterm birth, defined as occurring less than 32⁺⁰ weeks gestation. Preventative measures which prolong fetal gestation by 1 week, such as those proposed by this study, could save health services £939 million per year in England and Wales(5).

The insertion of a suture around the cervix under regional anaesthesia is an established management strategy in those women at high risk of preterm birth. There is little consensus on the optimal procedure, technique or timing of insertion. Its mechanism of action has been hypothesised as not only supportive but as reinforcing the immunological barrier which protects the fetus from ascending vaginal infection. The benefit of an ultrasound indicated cerclage following evidence of cervical shortening ($\leq 25\text{mm}$) on transvaginal ultrasound scan has been reported to demonstrate a significant reduction in delivery <35 weeks gestation compared with expectant management (6).

The primary risk factor for PTB in multiparous women is a previous PTB(7). Emerging evidence has shown an association between late miscarriage (LM) (14-24 weeks) and PTB in women with a history of full dilatation caesarean section (FDCS) at term, affecting approximately 13.5% of these women. This is hypothesised to be due to a uterine incision, which is inadvertently too low, in or near to effaced cervical tissue. This occurs because the cervix becomes continuous with the lower segment of the uterus at full dilatation and the anatomy can often be distorted. Disruption and scarring of this cervical tissue is thought to result in cervical incompetence in future pregnancies. The association between FDCS and LM/PTB has only recently been recognised and it presents a pressing clinical problem.

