Over 25% of all deliveries in the UK are by CS and up to 20% of in labour caesarean sections occur at full dilatation, which could affect up to 20,000 women in the UK per annum (8). These women have a six-fold increased incidence of subsequent preterm birth compared with women who undergo CS in the first stage of labour (adjusted odds ratio 5.8; 95% confidence interval 1.08-30.8)(3); 13.5% in comparison with 2%. This equates to around 2500 women per year in the UK. In women who lose a pregnancy, more than half will also go on to experience recurrent pregnancy losses in spite of intervention, compared to 14% of women with a history of preterm birth without previous FDCS (relative risk 3.06 95% confidence interval 1.22-7.71)(9). The relative risk of PTB in women with a previous emergency CS earlier in labour is unknown, however it is thought to be a continuum of risk, i.e. the later in labour the CS is carried out, the higher the risk of PTB in future pregnancies.

A screening programme to assess for cervical shortening in women with a previous FDSC is due to be implemented as part of new NHS commissioning guidance(1) and the revised *Saving Babies Lives Care Bundle*(2). It is unknown whether transvaginal cervical length screening for a short cervix predicts outcome in this group and there is currently limited evidence to inform optimal management of these women. It is also unknown whether first-line interventions for short cervix $\leq 25\text{mm}$ (vaginally-placed cerclages inserted in the distal cervix during pregnancy), used in other high-risk groups of women, is effective in this cohort. Preliminary data indicates that these interventions may be less efficacious, likely due to the injury having occurred in the proximal cervix, above the cerclage. A small retrospective analysis indicated that of 19 women who had experienced a LM/PTB subsequent to a FDSC and who then had a cerclage in the 3rd pregnancy, 10 (53%) still delivered <30 weeks gestation in comparison with 3% of a high-risk control group, who also had a cervical cerclage in situ after a LM/PTB (n=154).

This study has been developed in collaboration with the Preterm Birth Studies PPI Group at St Thomas' Hospital. They have confirmed that this issue is of vital importance to them and they will be consulted on all study literature and future directions associated with this project.

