4.1. CRAFT-OBS

Primary endpoint:

- i) Delivery < 37 completed weeks gestation (powered).

Secondary endpoints

- i) Adverse perinatal outcome, defined as a composite outcome of death (ante-partum/intra-partum stillbirths plus neonatal deaths prior to discharge from neonatal services)
- ii) Delivery <34 weeks gestation.
- iii) Gestation at delivery.
- iv) Late miscarriage (14⁺⁰-23⁺⁶ weeks).
- v) Healthcare use, e.g. appointments, hospital admission, cervical length, cervicovaginal fetal fibronectin levels, interventions.
- vi) Predictive modelling to evaluate the ability of CL and fFN to determine risk of preterm birth <34 and <37 weeks
- vii) Other maternal and fetal morbidities, as per COPOP core outcome set for preterm birth intervention studies(15).

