4.3. CRAFT-IMG

Primary endpoint:

- i. Alterations in imaging parameters between women with a full dilatation C-section in a previous pregnancy and either a cervix $\leq 25\text{mm}$ or a cervix $>25\text{mm}$ in this pregnancy which culminates in a preterm (<37 week) delivery.

5. Sample size and power calculation

All power calculations were performed by the trial statistician [name].

CRAFT-OBS: With estimated prevalence of 15% preterm birth rate prior to 37 weeks, and 16.2% of all deliveries being by emergency caesarean section; we will require data on 2200 women to estimate the event rate to 10% relative accuracy (e.g. 13.5% to 15.6%).

An average district general hospital has 4,000 deliveries per year, of which 648 (16.2%) might be by Emergency Caesarean. We aim to recruit 324 of these (50%) at a minimum of 7 study sites. At St Thomas' Hospital rather fewer deliveries (11%) are caesareans in labour; so we will aim for at least 20 sites, taking the assumptions above into account.

If we acquire data of cervical length and/or quantitative fetal fibronectin in this cohort, we will be able to validate these prediction tools. If we treat a short cervix of $\leq 25\text{mm}$, and a raised qfFN of $\geq 50\text{ng/ml}$ as positive tests, we anticipate a 75% sensitivity and 83% specificity from the literature for both tests (16).

Assuming 10% event rate, 1000 women (100 cases and 900 controls) would allow use to estimate the sensitivities of qfFN and CL to within 10% and the specificities to within 3% of the true value. The PPV would be estimated within 7% and NPV within 1.5% of their true values.

CRAFT-RCT: Pilot data indicates that at least 10% of all births and 70% of preterm births associated with FDCS occur before 34 weeks. In order to detect a reduction in this rate from 10% to 5% 474 women are required in each group to give 80% power. We will aim to recruit 500 in each arm in order to allow for 5% loss to follow-up.

CRAFT-IMG: We consider that the participation of 60 women in this sub-study will provide useful information for planning future research; this is achievable by recruiting at 2 sites (UCLH and St Thomas' Hospital): 30 women with cervix $>25\text{mm}$ and 30 women with cervix $\leq 25\text{mm}$ (15 women with cerclage, 15 women without).

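### Minor free improvement: the RCT's primary analysis does not use the minimisation factors, and the minimised risk-factor item leaves out previous non-PPROM births at 24-36 weeks

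*Combined protocol and SAP*

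**What the plan says.** **Allocation (section 7.4).** Women are allocated 1:1 by minimisation on gestation, BMI (below 30, or 30 and above) and a single combined item, "risk factor (previous premature delivery <24 weeks, PPROM, late miscarriage or previous cervical surgery".

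**Definitions.** The Professional Summary has "Preterm birth (PTB), birth before 37 weeks gestation", and section 1.1 uses the same 37-week limit. Section 4.1 has "Late miscarriage (14⁺⁰-23⁺⁶ weeks". Section 1.1 also states: "The primary risk factor for PTB in multiparous women is a previous PTB(7".

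**Eligibility (sections 6.1 and 6.2).** Neither list excludes a woman because of a previous birth at 24-36 weeks.

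**Analysis (section 8, CRAFT-RCT).** The section fixes intention to treat, delivery before 34 weeks as the main outcome, odds ratios and risk differences as effect measures, an NNT where appropriate, and a subgroup analysis by other risk factors for preterm birth. It does not mention the minimisation factors as covariates.

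**Sample size (section 5).** "In order to detect a reduction in this rate from 10% to 5% 474 women are required in each group", at 80% power, with 500 per arm recruited to allow for 5% loss.

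**The concern.** Two linked points arise.

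First, minimisation makes the arms more alike on the chosen factors than simple randomisation would. If those factors predict delivery before 34 weeks, an analysis that ignores them overstates the random variation between arms. Its confidence intervals are a little too wide and its test a little too cautious. The planned subgroup analysis does not correct this, because it asks whether the effect differs between subgroups and does not adjust the overall comparison.

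Second, the risk-factor item is narrower than the protocol's own account of risk. A premature delivery before 24 weeks is nearly the same event as a late miscarriage, so that component adds almost nothing. The repetition does no harm in a list where any one component counts. But a woman with a previous birth at 24-36 weeks, without PPROM, late miscarriage or cervical surgery, is minimised as having no risk factor.

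What is at stake is a small amount of precision, and the use of a prognostic factor that the protocol itself names and will already have on file.

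**Working it through.** **1. The plan's own figure.** Inputs from section 5: 10% versus 5%, 80% power. The significance level is not stated; two-sided 5% is assumed.

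- Uncorrected: n = [1.96·√(2·0.075·0.925) + 0.8416·√(0.10·0.90 + 0.05·0.95)]² / 0.05² = 434.4, so 435 per group.
- Continuity-corrected: n′ = (434.4/4)·[1 + √(1 + 4/(434.4·0.05))]² = 473.6, so 474 per group. This matches the plan.
- Allowing for loss: 474/0.95 = 499, rounded to 500. Expected analysed: 500·0.95 = 475 per arm.

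**2. Does either chi-square test reach 80%?** Exact power with 475 per arm is 84.2% for the uncorrected chi-square and 81.0% for the corrected one. Both exceed 80%.

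**3. Cost of ignoring the minimised risk-factor item.** The documents give neither its prevalence nor its strength. Assumed: prevalence 10-30%, odds ratio 2-6. If the factor is balanced by design, the unadjusted standard error is too wide by the ratio √[p(1−p) / Σ wₛpₛ(1−pₛ)]. Here p is the overall risk, and wₛ and pₛ are the share and risk of each stratum. The true type I error is then 2Φ(−1.96 × ratio).

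| Assumed prevalence, OR | Overall p | Risk without / with factor | p(1−p) | Within-stratum | SE ratio | Type I error |
|---|---|---|---|---|---|---|
| 10%, 2 | 7.5% | 6.9% / 12.9% | 0.06938 | 0.06905 | 1.002 | 4.95% |
| 30%, 6 | 10% | 4.6% / 22.5% | 0.09000 | 0.08326 | 1.040 | 4.16% |

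The standard error is therefore about 0.2-4.0% too wide.

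**4. Effect on power.** This was simulated with minimisation (biased coin 0.8) and 950 women. Assumptions: gestation split at 20 weeks for allocation, uniform over 14-24 weeks, with log odds −0.1 per week; BMI of 30 or more in 25%, odds ratio 1.3. The Monte Carlo standard error is about 0.35 points.

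| Risk-factor prevalence, OR | Unadjusted power | Logistic, three minimisation factors | Gain |
|---|---|---|---|
| 10%, 2 | 83.9% | 83.8% | none |
| 30%, 6 | 85.2% | 86.7% | 1.5 points |

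Across scenarios the simulated type I error was 4.4-5.1% for the uncorrected chi-square, 4.8-5.0% for the proposed logistic model and 5.1-5.4% for the standardised risk difference. A separate, simpler simulation with one binary factor (prevalence 10% or 20%, odds ratio 2 or 4) found a largest gain of about 1 point (83.5% to 84.7%).

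**5. The births left out at 24-36 weeks.** Their prevalence is not in the documents; 2-13.5% is assumed. The upper value borrows the figure for late miscarriage and preterm birth together after FDCS (section 1.1: "affecting approximately 13.5% of these women"). It is probably generous, because late miscarriages and PPROM births are already in the item and section 6.1 excludes women already started on progesterone, a cerclage or a pessary. With prevalence q and 475 per arm, the standard deviation of the chance difference between arms is √[2q(1−q)/475]: 0.9 points at q = 2%, 1.4 at 5% and 2.2 at 13.5%. That is ordinary randomisation noise, centred on zero. How far it moves the treatment effect depends on the excess risk in these women, which the documents do not give.

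**6. Can the data support the model?** Expected events: 475·0.10 + 475·0.05 = 71. The model has five coefficients (treatment, gestation, BMI group, risk-factor item, previous preterm birth), so about 14 events per coefficient. At 2% prevalence, however, only 950·0.02 = 19 women would carry the last covariate, so a fallback is needed.

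**The case against.** The strongest reply is that little is at stake. Randomisation protects validity, the gain in power is at most about 1.5 points and close to zero in mild scenarios, and section 8 already fixes the population, outcome and effect measures. The linear gestation term and the separate covariate are reasonable choices rather than corrections of an error, and an amendment across at least 41 hospitals (section 3.2) takes effort. All of this stands, and it is why the point is minor. Some births at 24-36 weeks are also captured through PPROM, so the gap is narrower than the wording first suggests.

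A reader might infer four stronger things that the documents do not support.

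- **That the 24-week limit biases the trial.** It does not. An unminimised factor is still randomised.
- **That the omission matters a great deal, because of women "who then had a cerclage in the 3rd pregnancy, 10 (53%) still delivered <30 weeks gestation".** That is 10 of 19 women. The group mixes late miscarriage, which the item already covers, with preterm birth. All had a cerclage, and the outcome is delivery before 30 weeks. The comparison figure, "compared to 14% of women with a history of preterm birth without previous FDCS", describes recurrent pregnancy loss, not delivery before 34 weeks. Neither can be used to size the effect here.
- **That the trial is underpowered because 474 comes from a continuity-corrected formula and section 8 names no test.** Either chi-square version exceeds 80% with 475 per arm. The choice matters only near the threshold: 47/475 versus 30/475 gives p = 0.043 uncorrected and 0.057 corrected. The unnamed test and the missing gestation cut-points are missing detail, not errors.
- **That leaving adjustment open inflates false positives.** For the minimisation factors, choosing between the unadjusted and adjusted test causes no inflation.

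**Conclusion.** The point holds as a minor free improvement. An analysis that ignores the minimisation factors is valid but slightly conservative: standard error about 0.2-4% too wide, type I error about 4.2-5.0%, power loss about 0-1.5 points. These sizes rest on an assumed risk-factor prevalence of 10-30% and odds ratio of 2-6, and on the planned 10% versus 5% with 475 analysed per arm.

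The narrow risk-factor item is inconsistent with the protocol's own definition of preterm birth and its own statement of the main risk factor. Its consequence is limited to ordinary chance imbalance, and no figure is put on the resulting shift in the treatment effect. Randomisation and the sample size are unaffected.

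**What to change.** **Section 8.** Make the primary analysis a logistic model for delivery before 34 weeks, by intention to treat, adjusted for:

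- gestation at randomisation (continuous, linear);
- BMI group;
- the risk-factor item as minimised;
- previous preterm birth at 24+0-36+6 weeks (yes/no), derived from the obstetric history collected under section 7.3. Keeping this separate avoids grouping a 36-week birth with a second-trimester loss.

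Report the adjusted odds ratio and a standardised risk difference with 95% confidence intervals, and take any NNT from the risk difference. State the significance level, the test of the treatment coefficient and the variance method for the risk difference in the same text. Use the unadjusted risk difference as the sensitivity analysis, not the unadjusted odds ratio, because adjusted and unadjusted odds ratios estimate different quantities. If the previous-preterm-birth covariate is too sparse, drop it, or use a Mantel-Haenszel risk difference stratified by the risk-factor item.

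**Section 7.4.** Reconcile the 24-week limit with the protocol's definition of preterm birth. Leave past allocations unchanged.

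**Cost.** A protocol amendment under section 10.6: chief investigator approval and notice to the co-sponsors, plus REC, regulator and local R&D approval if it is substantial. It needs one RedCap field definition and a few lines of analysis text, with no new data item and no change to the 474 per group (500 recruited). It must be done before outcome data by arm are seen.

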1.2. Rationale for study

The overall aim of the CRAFT project is to investigate the role of previous in labour caesarean section in future preterm birth risk and management strategies.

[figure not shown]
CRAFT-OBS will determine the risk of spontaneous PTB in women with previous CS in labour. We will use any data on qfFN testing and CL measurements to validate current predictive modelling of preterm birth using these tests, which are the most commonly used predictors of PTB. Participants whose CS was carried out at full dilatation, and whose cervix measures $<25\text{mm}$ will also be invited to take part in the CRAFT-RCT (n=1000) and CRAFT-IMG (n=30). Participants with a history of FDSC and a cervix $\geq 25\text{mm}$ will be offered the opportunity to participate in CRAFT-IMG (n=30).

CRAFT-RCT will determine whether an ultrasound-indicated cervical cerclage is an effective management option in women with cervical shortening following a FDSC. It will also determine if a shortening cervix predicts outcome in this cohort. If it is demonstrated to be ineffective, further research will be required regarding alternative screening and treatment options. This may include imaging the cervix pre-pregnancy for evidence of cervical defects and/or offering a transabdominal cerclage (TAC) in the proximal cervix pre-pregnancy above the level of hypothesised defects.

CRAFT-IMG will inform development of methods for identifying cervical defects in women with a history of CS in labour. We will explore the value of scanning the cervix for scars/areas of abnormality to indicate which women are most at risk of adverse outcomes and require further monitoring and therapy. Currently the ultrasound-assessed CL is the only parameter used in

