6.2. Inclusion and exclusion criteria specific to CRAFT-RCT

Inclusion criteria:

- Pregnant women between 14⁺⁰ and 23⁺⁶ weeks gestation with a history of FDSC.
- Short cervix (≤ 25 mm) on transvaginal ultrasound scan.

Exclusion criteria:

- Women with persistent fresh vaginal bleeding evident on speculum examination.
- Women with visible fetal membranes evident on speculum examination or open cervix on ultrasound scan.
- Women with severe abdominal pain/evidence of sepsis (as judged by attending clinician).
- Known significant congenital or structural or chromosomal fetal abnormality.
- Suspected or proven rupture of the fetal membranes at the time of recruitment.

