7.1. Identification of participants

CRAFT-OBS

We will recruit pregnant women who are booked for their delivery at participating centres who provide written informed consent to participate in the study and who meet the study eligibility criteria.

Women who have previously had an emergency caesarean in labour will be identified through their booking appointment or scan appointments by the direct care midwife, doctor, sonographer and approached with information about this observational study. Clinical midwives, doctors or sonographers will highlight eligible women to the research team. The research team will then be able to discuss the research with patients if they are eligible at the time of their first trimester or second trimester scan.

CRAFT-RCT

Women participating in CRAFT-OBS will be eligible for CRAFT-RCT if they are found to have a cervix ≤ 25 mm prior to 23⁺⁶ weeks gestation with a history of FDCS. Women with a previous full dilatation caesarean section will be identified by a member of the direct care team and referred for cervical surveillance as per new guidance (1,2). The research team will check relevant hospital records when patients are consented in order to confirm a previous full dilatation caesarean section occurred. If these records are not available for review the patients will be excluded. Eligible women will be informed about the trial by a doctor, sonographer or midwife if their transvaginal ultrasound confirms a short cervix (≤ 25 mm). Members of the research team

Study Protocol: **Cerclage After Full-dilatation caesarean-section**

IRAS ID:261294

REC: REC 19/LO/1270

Version 2.0

Date: 10.09.19

(midwives, doctors and scanning practitioners) can then discuss the research further and consent women.

- If a woman is randomised to a cervical cerclage, the procedure needs to take place within 7 days of diagnosis of cervical shortening and removed around 37 weeks gestation. She will also have regular scan surveillance in accordance with local protocols. Rescue cerclage can be offered in cases of cervical opening with exposed membranes as per local guidelines. Targeted admission for bedrest and steroids can also be offered as per clinician practice and local protocols.

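### Section 8 plans accuracy statistics and an AUC for cervix ≤25 mm under CRAFT-RCT, but ≤25 mm is the entry criterion, so randomised women alone cannot show whether the cut-off predicts delivery <34 weeks

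*Combined protocol and SAP*

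**What the plan says.** - Section 8, CRAFT-RCT paragraph, lists among its analyses the following: "prediction of delivery <34 weeks gestation (cervix ≤ 25 mm will be calculated along with area under the curve". Cervical length and fibronectin appear again in the next sentence: "We will also validate our current predictive tools of cervical length and fetal fibronectin in this population". No other analysis set is named, and CRAFT-OBS prediction has its own paragraph.
- Section 6.2, RCT inclusion: "Short cervix (≤ 25 mm) on transvaginal ultrasound scan". Section 7.1 agrees: "Women participating in CRAFT-OBS will be eligible for CRAFT-RCT if they are found to have a cervix" of 25 mm or less before 23+6 weeks, with a previous full-dilatation caesarean (FDCS). Section 3.2 words the threshold as <25 mm, which also leaves no woman above the cut-off.
- Section 1.2, of CRAFT-RCT: "It will also determine if a shortening cervix predicts outcome in this cohort".
- The Professional Summary lists as unknown whether the 25 mm "cut-off is a reliable predictive measure of risk in women following in labour CS", and section 1.1 says: "It is unknown whether transvaginal cervical length screening for a short cervix predicts outcome in this group".
- Prediction is also a CRAFT-OBS endpoint (section 4.1): "Predictive modelling to evaluate the ability of CL and fFN to determine risk of preterm birth" at <34 and <37 weeks. The end of section 5 plans ROC curves with cervical length as a continuous variable.

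**The concern.** A diagnostic cut-off can be assessed only where both test results occur. Sensitivity needs women who delivered early despite a longer cervix, and specificity and NPV need women with a longer cervix who did not. The RCT excludes both groups at entry, yet section 8 asks it for accuracy statistics and section 1.2 gives it the prediction question.

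At stake is a question the protocol itself calls open. A table from randomised women alone would be fixed in advance, and an AUC from the short range could be misread as poor screening performance. CRAFT-OBS can supply women with longer cervices, but randomised women come out of CRAFT-OBS. No section says whether they enter its prediction analysis, or how those allocated cerclage are handled. That choice changes the answer.

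**Working it through.** **Inputs.** Section 5, CRAFT-OBS prediction paragraph: 1000 women, 10% event rate (100 cases, 900 controls), sensitivity 75%, specificity 83%. Section 5, CRAFT-RCT: 10% against 5%, 474 per arm, 500 recruited. Section 7.4: 1:1 allocation. Half-widths are 1.96·√(p(1−p)/n) unless stated.

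**1. The plan's own precision figures.** TP = 75, FN = 25, FP = 153, TN = 747.
- Sensitivity: p = 0.75, n = 100, ±8.5 points (stated: within 10%).
- Specificity: p = 0.83, n = 900, ±2.5 (stated 3%).
- PPV = 75/228 = 32.9%, ±6.1 (stated 7%).
- NPV = 747/772 = 96.8%, ±1.2 (stated 1.5%).

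All four agree with section 5. They rely on 25 + 747 = 772 test-negative women per 1000.

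**2. The same table in the RCT.** With 1000 randomised women at the planned rates, events = 500×0.10 + 500×0.05 = 75.
- TP = 75, FP = 925, FN = 0, TN = 0.
- Sensitivity = 75/75 = 100%; specificity = 0/925 = 0%; NPV = 0/0; AUC = (1 + 0)/2 = 0.50.

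Only PPV carries information, and it is simply the event rate: 7.5% pooled, 10% under standard care. The other results do not depend on the rates assumed.

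**3. Continuous length (illustrative).** Assume normal lengths with equal SD in cases and controls, passing through 75%/83% at 25 mm. The AUC is about 0.88 over the full range and about 0.74 among women ≤25 mm (0.66 to 0.79 for a case:control SD ratio of 0.75 to 1.25). The documents give no length distribution.

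**4. Handling of randomised women in a full-range analysis.** Per 1000 on section 5's inputs, assuming all 228 short-cervix women are randomised:
- Cerclage arm dropped, no reweighting: TP = 37.5, FP = 76.5. Sensitivity = 37.5/62.5 = 60%; specificity = 747/823.5 = 91%. This distortion arises even if cerclage does nothing.
- Arms pooled, cerclage assumed to halve risk: TP = 37.5 + 18.75 = 56.25, FP = 171.75. Sensitivity = 56.25/81.25 = 69%; specificity = 747/918.75 = 81%; PPV = 56.25/228 = 25%. With no cerclage effect, pooling does no harm.
- Cerclage arm dropped, standard care given weight 2: TP = 2×37.5 = 75, FP = 2×76.5 = 153. The 75%, 83% and 33% are recovered.

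**5. Precision of the weighted analysis** (sensitivity and specificity by simulation of 1000 women with balanced allocation):

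| Short-cervix women randomised | Sensitivity | Specificity | PPV |
|---|---|---|---|
| No arm removed | ±8.5 | ±2.5 | ±6.1 |
| Half | ±8.9 | ±2.6 | ±7.5 |
| All | ±9.3 | ±2.8 | ±8.6 |
| Stated in section 5 | 10% | 3% | 7% |

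PPV, all randomised: n = 228/2 = 114. Half randomised: 57 women at weight 2 and 114 at weight 1, so effective n = 228²/(57×4 + 114) = 152.

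With the planned 474 standard-care women, the PPV half-width is ±2.7 points at a 10% rate and ±4.2 at 33%. Both rates are shown because section 5's prediction inputs imply 33% in test-positive women while its RCT calculation uses 10%.

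**The case against.** The strongest reply is that CRAFT-OBS already covers prediction. It includes longer cervices, has prediction as an objective and endpoint, carries the precision calculation, and section 5 specifies continuous length. On this view section 8 contains one loosely worded, misplaced sentence. That limits the damage, but section 1.2 gives the question to the RCT as well, and nothing says how randomised women enter the CRAFT-OBS analysis. Reading section 1.2's cohort as all women with previous FDCS leaves the same gap.

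A second reply is that the 100%/0% result applies to the qualifying scan only. Sections 3.2 and 7.3 admit women whose cervix is or becomes short, so some may have earlier scans above 25 mm. This stands as a caveat: the scan used must be stated. Every randomised woman has still been selected for later shortening.

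Third, the standard-care arm is not untreated. Section 7.1 allows rescue cerclage and targeted admission there, so its event rate describes the cut-off under standard care.

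Stronger readings are tempting but not supported:
- That the planned AUC must be 0.50. Section 8 does not say which AUC is meant, and one of continuous length is not fixed at that value.
- That the plan pools the arms and so biases accuracy. It is silent on pooling, and the size of any bias depends on an unknown cerclage effect.
- That fibronectin validation fails too. Fibronectin is not an entry criterion, so both results can occur, though only among short-cervix women.

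**Conclusion.** The point holds for a secondary analysis. In randomised women, at the qualifying scan, the ≤25 mm cut-off has sensitivity 100%, specificity 0%, AUC 0.50 and undefined NPV. This follows from the entry criterion and needs no assumption. A continuous-length AUC in the same women is estimable but confined to the short range. Neither tells whether a shortening cervix predicts outcome.

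The restricted AUC (0.74 against 0.88) and the pooled-arm figures (69%, 81%, 25%) are illustrations resting on assumptions the documents do not state. The 60%/91% result for dropping the cerclage arm unweighted needs only section 5's inputs and all short-cervix women being randomised.

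A reader might infer that the trial's main result is compromised. It is not: the intention-to-treat comparison of delivery <34 weeks, the sample size and the section 4.2 endpoints do not use this analysis. The amendment is worth making because the programme collects data that can answer the question, and section 8 as written would not use them for it.

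**What to change.** 1. Remove the ≤25 mm accuracy and AUC analysis from the RCT-only set. Estimate it in all women with previous FDCS and a measured cervical length, including those >25 mm, enrolled through CRAFT-OBS. State that the AUC uses continuous length, and which scan is used.
2. Leave out the cerclage arm and give standard-care women weight 2, which follows from 1:1 allocation. Keep short-cervix women who were not randomised (section 7.3) at weight 1.
3. If a sensitivity analysis leaves out non-randomised women who received a cerclage, label it as conditioning on treatment given after the test.
4. Within the RCT, report for this cut-off only the standard-care event rate, described as the PPV under standard care, which may include rescue cerclage.

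**Cost.** Revised analysis wording and a weighted analysis; no new data. Precision falls because test-positive women are removed. On section 5's 1000-woman inputs the sensitivity and specificity targets are still met, but the 7% PPV target is not, whether half or all short-cervix women are randomised. If the planned 474 standard-care women are reached, PPV is comfortably inside 7 points at either rate considered. The plan should state which precision it now expects.
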